6.0. Definition of Study Samples

6.1. Participant Inclusion and Exclusion Criteria

This study will employ a population-based recruitment approach in which the individuals who are invited/recruited to potentially participate in the study will be identified based on the following electronic health records (EHR)-based criteria.

Participant Inclusion Criteria

Individuals must first meet these EHR-based criteria in order to be invited to be screened for participation.

1. Active/enrolled in one of the 4 participating integrated health care systems at the time of query and for the prior 360 days
2. Age 18 years or older (based on date of birth)
3. English speaking or do not need interpreter services
4. Have at least 1 [at Essentia] or at least two which are >60 days apart [at KP sites] outpatient pain-related health care encounters with nonmalignant musculoskeletal pain diagnoses [as determined by ICD10 codes for any of the following: back- neck-, limb/extremity-, joint-pain, arthritic disorders, fibromyalgia, headache, orofacial/temporomandibular pain, or musculoskeletal pain]¹⁴ within the past 360 days
5. Do not have an encounter for surgery related to common musculoskeletal pain conditions (e.g., joint replacement, spinal fusion, carpal tunnel release surgery) [as determined by CPT and/or ICD-10 codes] within the past 60 days
6. Do not have two or more separate encounters with a malignant cancer diagnosis other than non-melanoma skin cancer [as determined by ICD-10 codes] within past 60 days
7. Do not have ICD-10 code(s), CPT code(s) or department/provider encounters indicating receipt of hospice or other palliative care within the past 360 days
8. Do not have ICD-10 codes indicating severe cognitive impairment precluding participation in a behavioral/ lifestyle change program

Note: At the KPWA site only, one additional EHR-based exclusion criterion will be applied, which is: Do not have ICD-10 codes indicating opioid use disorder (OUD). This criterion is being applied because there is another HEAL study being conducted at KPWA that focuses on treating individuals with pain and OUD specifically.

Individuals who meet the above EHR criteria will be invited to respond to screening questions and must meet the following inclusion criteria:

1. Have high-impact chronic pain (as indicated by self-report of having pain on most or every day in past 3 months and pain limiting life or work activities on most or every day in past 3 months)⁹
2. Have persistent pain (as indicated by self-report PEG score of ≥ 12)
3. Be able to participate in either of the active interventions (i.e., have internet and phone access required for accessing treatments)

Participant Exclusion Criteria

Individuals screened who meet the inclusion screening criteria (and the initial EHR criteria described above) cannot endorse any of the following exclusion criteria:

1. Have received CBT for pain or pain-related psychoeducation or behavioral skills training within in the past 6 months (in-person, by phone or videoconference, or online)
2. Currently receiving or will be starting CBT for pain or pain-related psychoeducation or behavioral skills training in the next month (in-person, by phone or videoconference, or online)

3. Currently receiving or will be starting inpatient or intensive outpatient services for substance use disorder in the next month
4. Have a planned/scheduled surgery in the next 12 months related to pain condition

6.2. Intent-to-Treat (ITT) Sample

As the primary analysis, all effectiveness outcome measures are analyzed under the ITT. Under this principle, each eligible subject is analyzed according to the treatment group to which they were assigned at the time of randomization.

Modified intent-to-treat will not be employed in this protocol.

6.3. Safety Analysis Sample

All randomized subjects will be included in the primary safety analysis sample. Secondary analyses will exclude those in the intervention groups who were deemed as ineligible post-randomization and therefore not able to continue in the intervention group (e.g., dementia noted after randomization).

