Because the patients who participate in the RESOLVE study will be older and have co-morbid health conditions, it is expected that subjects will experience inpatient hospitalizations, which are unrelated to study participation, during the course of the study. In addition, it is expected that deaths, which are also unrelated to study participation, might occur among study enrollees based on prior studies. Specifically, in the study PI's recently completed pragmatic trial, PPACT, which provided an intensive in-person behavioral intervention and enrolled 850 patients with chronic pain, there were 12 deaths during the study, all unrelated to study participation, and 287 hospitalizations (116 for intervention participants and 171 for usual care).

SAEs will be systematically assessed every 6 months for active study participants based on electronic health records (EHR) data.

- Each clinical site will query active participants' electronic health records data every 6 months (in alignment with the DSMB meeting schedule) to identify any deaths or hospitalizations throughout the interval of active participant enrollment in the trial.
- An independent physician within each health care system/clinical site will conduct a chart review for each death and hospitalization to assess its potential relatedness to study procedures and interventions.
- The summary of SAEs and findings of these reviews will be submitted to the DCC.

In addition to the semi-annual EHR queries, SAEs may be identified by participant self-report. If this occurs, the event will be documented and reviewed by the independent physician as part of the semi-annual review described above.

12.1.3 *Definition of Adverse Events of Special Interest (AESI)*

This protocol will not collect solicited adverse events of special interest (AESI). There is no clinical or empirical basis for hypothesizing that either of the active interventions would increase risk of AESIs. In addition, the unequal contact with study staff among participants in the three study arms inherently results in differential opportunities for ascertainment of "events." Therefore, between-group comparison of adverse events reported to or discovered by study staff would be biased and hence not meaningfully interpretable or actionable.

12.1.4 *Severity of Adverse Events*

For an AE, the following guidelines will be used to describe severity:

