15.2 Populations for Analyses

All analyses will be conducted following an intent-to-treat approach, including all individuals randomized regardless of their engagement with or exposure to the intervention.

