19.2. Serious Adverse Events

For this comparative effectiveness trial, a serious adverse event (SAE) is defined as an event that:

- Results in death during a patient's active participation in the trial.
- Results in inpatient hospitalization during a patient's active participation in the trial. (Planned hospitalization scheduled before the enrollment of a study participant is not an SAE.)

Given the relatively large sample size for this trial (N=2,331), we expect some inpatient hospitalizations and deaths to occur among participants. However, none of our previous trials using these types of behavioral interventions have identified study related SAEs.

The following is a summary of the procedures that will be used for monitoring and reporting SAEs; further detail is provided in the DSMP.

Each clinical site will query active participants' electronic health records data every 6 months (in alignment with the DSMB meeting schedule) to identify any deaths or hospitalizations throughout the interval of active participant enrollment in the trial.

For deaths, the date of the event and information needed to facilitate the chart review (described below) will be extracted. For hospitalizations, diagnoses, reason for admission, and length of stay will be extracted to allow the determination of potential relatedness.

A physician within each health care system/clinical site will conduct a chart review for each death to assess its potential relatedness to study procedures and interventions. The findings of each review will be entered into a DSM electronic data capture system hosted by the DCC.

Hospitalizations will not be chart reviewed routinely, however if reports suggest possible relatedness, chart reviews will be conducted on all or a subset of hospitalizations based on DSMB recommendation.

A report summarizing the SAEs and chart reviews will be provided to the DSMB at regular meetings. Any SAEs that are identified during these semi-annual reviews which meet the criteria for immediate reporting to the IRB, NIA PO, and DSMB will be reported according to DSMP procedures.

In addition to the semi-annual EHR queries, SAEs (hospitalizations and deaths) may be identified by participant self-report. If this occurs, the event will be documented and reviewed by the designated physician at the clinical site as part of the semi-annual review described above; it will not be reviewed at the time of reporting.

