19.4. Descriptive Analyses

The safety analyses will be performed using descriptive statistics to quantify hospitalizations and deaths (SAEs) by usual care control arm and separately by each intervention arm. As the study is not powered to test for non-inferiority of the safety events by exposure to the interventions compared to the usual care control, no statistical tests will be performed on group differences in the SAE safety.

19.5. Summary of AEs and SAEs by MedDRA Code and Grouped by Organ System

Because this trial focuses exclusively on behavioral interventions MedDRA codes covering pharmaceuticals, biologics, vaccines, and drug-device combination products are not applicable.

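### The secondary safety sample removes post-randomization ineligibles from the active arms only; separately, the Protocol and SAP differ on whether each hospitalization is chart-reviewed

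*SAP*

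**What the plan says.** **Safety sample.** SAP 6.3 begins: "All randomized subjects will be included in the primary safety analysis sample". It continues: "Secondary analyses will exclude those in the intervention groups who were deemed as ineligible post-randomization". The stated reason is that such people cannot go on with the intervention, and dementia discovered later is the example. Nothing is said about usual care participants found ineligible in the same way. Under SAP 19.4 the safety analyses are to "quantify hospitalizations and deaths (SAEs) by usual care control arm and separately by each intervention arm"; SAP 19.3 and 19.4 rule out formal tests. Protocol 15.2 states: "All analyses will be conducted following an intent-to-treat approach, including all individuals randomized". SAP 2.0 gives the SAP precedence over the Protocol's analytical plans.

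**SAE review.** In Protocol 12.1.2, an independent physician at each site "will conduct a chart review for each death and hospitalization to assess its potential relatedness to study procedures and interventions". SAP 19.2 keeps routine review for deaths but says: "Hospitalizations will not be chart reviewed routinely". For hospitalizations, the SAP has sites extract the diagnoses, why the patient was admitted and how long the stay lasted, so that relatedness can be judged. Chart review of some or all of them follows only if reports point to a possible link and the Data and Safety Monitoring Board (DSMB) recommends it. The SAP change log (10/19/20) records that routine hospitalization review was removed with DSMB approval. SAP 19.3 tabulates SAEs by arm and relatedness, and Protocol 13.1 triggers notice to the DSMB chair for unexpected, related SAEs.

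**The concern.** Randomization makes the arms comparable, including in the share of people who should not have been enrolled. Removing those people from two arms and leaving their counterparts in the third gives up that comparability. Someone whose dementia comes to light after entry plausibly has a higher risk of hospitalization or death, so the rule would tend to make the interventions look safer. Discovery may also depend on contact with staff: Protocol 12.1.3 and SAP 19.1 themselves decline comparisons of staff-reported events because contact differs by arm.

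The second matter is a conflict between two current texts. A reader of the Protocol would believe that every hospitalization's relatedness rests on a physician's chart review. Under the SAP, most would not. Relatedness feeds both a by-arm table and a notification rule, so the process behind it should be stated once and consistently.

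**Working it through.** The plan gives no figure for either point, so there is none to reproduce. The size of the first can only be shown under assumptions.

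**1. One-sided exclusion**

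Inputs: 777 per arm (SAP 5.0, Protocol 15.1). Assumed, because the documents do not give them: *f*, the share of an active arm removed (0.5% to 3%), and *k*, the event rate of those removed relative to the rest (2 to 4).

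Let *r* be the rate in those kept. The all-randomized rate is (1 − f)·r + f·k·r = r·(1 − f + kf), and the trimmed rate is r. So

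apparent / all-randomized = 1 / (1 − f + kf).

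| f | k | Removed of 777 | Ratio |
|---|---|---|---|
| 0.5% | 2 | 3.9 | 1/1.005 = 0.995 |
| 1% | 3 | 7.8 | 1/1.02 = 0.980 |
| 2% | 3 | 15.5 | 1/1.04 = 0.962 |
| 3% | 4 | 23.3 | 1/1.09 = 0.917 |

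In absolute terms, take f = 2%, a 20% rate in those kept and 60% in those removed (also assumed), with no true arm difference. Usual care shows 0.98 × 20% + 0.02 × 60% = 20.8%; a trimmed active arm shows 20.0%.

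For a 5% understatement, f = (1/0.95 − 1)/(k − 1) = 5.26%, 2.63% or 1.75% for k = 2, 3, 4. Times 777, that is about 41, 20 or 14 people in one active arm.

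Deaths: Protocol 12.1.2 cites a prior trial with 12 deaths among 850 enrolled. That rate gives 12/850 × 777 = 10.97 deaths per arm (illustrative only, since no follow-up length is given). The expected share of deaths removed is fk/(1 − f + kf). At f = 1%, k = 3 this is 0.03/1.02 = 2.9%, or 0.32 deaths per arm; at f = 3%, k = 4 it is 0.12/1.09 = 11.0%, or 1.2 deaths. The rate ratio is the same as for hospitalizations with the same f and k.

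Applying the same rule to no arm makes the artificial difference zero.

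**2. SAE review, side by side**

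- Deaths: routine chart review in both documents.
- Hospitalizations: routine chart review in Protocol 12.1.2; in SAP 19.2, extracted record data, with chart review only on DSMB recommendation.
- Event mix in the same prior trial: 116 + 171 = 287 hospitalizations and 12 deaths, 299 in total. Hospitalizations are 287/299 = 96.0%; deaths are 12/299 = 4.0%. With that mix, routine chart review covers all SAEs under one text and about 4% under the other, before self-reported events and any DSMB-requested reviews. This measures chart review only, not whether relatedness is judged.
- Does either document settle it? The SAP 2.0 precedence clause refers to analytical plans. SAP 19.0 sends the reader back to the Protocol, which holds the differing rule, and to the DSMP, which was not supplied. The visible Protocol log has entries on seven dates after 10/19/20 (11/10/20, 11/23/20, 11/24/20, 03/22/21, 03/31/21, 02/24/22, 11/10/22), and none lists Section 12. So neither text resolves the difference.

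**The case against.** On the first point, the exclusion is tied to being unable to continue an intervention, and usual care has no sessions to discontinue, so a literal counterpart does not exist. SAP 19.4 does not mention the secondary sample, so its comparison with untrimmed usual care is an inference. The all-randomized sample remains primary and nothing is tested. All of this is fair and limits the severity. It does not rescue the rule: a criterion that can only operate in the active arms is the problem, and SAP safety summaries are by arm.

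On the second point, the change was deliberate and DSMB-approved, and the SAP says what data inform relatedness. Self-reported SAEs also go to the site's designated physician. The DSMP may name who judges the rest. That leaves a mismatch of text and possibly an unnamed assessor. The mismatch stands whatever the DSMP says, because the current Protocol still states the other rule.

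A reader might also cite SAP 6.2: "Modified intent-to-treat will not be employed in this protocol". That section concerns effectiveness outcomes, so it shows no conflict with a safety sample. Protocol 15.2, which covers all analyses, does.

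**Conclusion.** Both points hold and both are minor. The one-sided exclusion would understate active-arm SAE rates in a secondary, descriptive display by roughly 0.5% to 8% for f = 0.5% to 3% and k = 2 to 4. This rests on those assumed values and on the removed people having above-average risk; the documents give none of these. The primary all-randomized safety results and the effectiveness results are untouched. The SAE review conflict is a plain inconsistency between two current texts.

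Four stronger readings are tempting, and the documents do not support them:

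- That relatedness of hospitalizations without chart review has no basis. SAP 19.2 lists record data extracted for that judgement, so dropping relatedness from the tables is not warranted.
- That the differing review rules bias the comparison between arms. Nothing in either text makes review depend on arm.
- That death counts are more exposed to the exclusion. Small counts add noise, but the expected ratio follows the same formula.
- That the trial's safety conclusions are compromised. The primary sample keeps everyone randomized.

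**What to change.** **SAP 6.3:** delete the secondary exclusion, so that every by-arm safety comparison uses all randomized participants. Extending the exclusion to all arms by re-running the eligibility code list ("Do not have ICD-10 codes indicating severe cognitive impairment precluding participation", SAP 6.1) would be a weaker remedy. Those codes already bar entry, codes recorded later depend on contact with care, including hospital care, and the list would miss other reasons for ineligibility.

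**SAE review:** reconcile Protocol 12.1.2 and 13.1 with SAP 19.2, SAP 19.3 and the DSMP, and record the result in the Protocol's change log. This review takes no view on which rule is right. State who determines relatedness for hospitalizations that are not chart-reviewed, unless the DSMP already does.

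**Cost:** wording only; no new data from participants and no new analysis.

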6.4. As-Treated Sample

The potential for cross-overs in this study is minimal; however, in the case of participants randomized to usual care who receive CBT outside of the study intervention, a per-protocol sample may be constructed (if greater than 10% cross-over from UC to receive CBT) and examined in which treatment-as-received is analyzed.

7.0. Definition of Treatment Adherence

Treatment adherence is defined as completing at least 6 of the 8 total sessions for each of the active intervention arms.

8.0. Randomization

After completion of the baseline data collection, study participants will be individually randomized in equal ratio to one of the three study arms.

Randomization will be stratified on:

Variable	Source
Sex	Sex from electronic health record (Male vs. Female or Other)
Pain severity score	Score on BPI-SF from baseline survey (< 7 vs. ≥ 7)
Clinical site	KPWA, KPNW, KPGA, Essentia
Rural/medically underserved residency	Residency geocode for Census Tract from electronic health record

Within each stratum, to contain concealment and balance randomization over time, a random permuted block design will be used with random variable block sizes of 3, 6, or 9 to ensure approximately equal accrual into the three study arms.

The TIN JHU/Tufts Lead biostatistician will develop the randomization scheme and the TIN Utah DCC will implement the scheme using the appropriate statistical software. The scheme to be implemented will be integrated into the study centralized tracking system.

Randomization will be conducted by KPWHRI research staff within the study centralized tracking system after consent and baseline assessment completion.

9.0. Blinding

Masking occurs at 2 levels: 1) masking to treatment assignment, i.e., not knowing which of the 3 treatment arms a participant has been assigned to in the study; and 2) masking to outcomes data, meaning not having access to follow-up study data individually, in aggregate or by treatment arm.

It is not feasible for participants to be masked to treatment arm assignment due to the type of intervention. The PI and select Co-Investigators and study staff who are involved in the administrative oversight of the study and/or delivery of the interventions will also be aware of treatment assignment but masked to outcomes data. Primary and secondary outcome assessors will be masked to treatment assignment but cannot be masked to individual outcomes data.

10.0. Multiplicity

We have one primary outcome: minimal clinically important difference (MCID) in pain severity at 3 months. To control for multiple comparisons due to 3 intervention groups we will apply Fisher's Least Significant Difference approach in which first an omnibus Wald test for any statistically significant difference between the three groups is evaluated at the 0.05 alpha level and the pair-wise differences are then evaluated, each using two-sided alpha=0.05, only if the omnibus test is statistically significant. In addition, secondary analyses will use a similar approach as that described for the primary outcome to control for the three group comparisons.

For safety outcomes, multiplicity will not be considered since this study was not powered to observe safety.

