15.3 General Approach to Statistical Analyses

All confidence intervals and p-values will be two-sided and statistical significance at the 0.05 level.

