15.6 Secondary Effectiveness Analyses

Secondary Outcomes (Aim1a) Primary Statistical Hypotheses: Those in both active intervention conditions will show greater improvements in overall pain severity, pain intensity (MCID and overall), pain-related interference (MCID and overall) and related quality of life outcomes (social role functioning, physical functioning, and patient global impression of change) relative to those receiving usual care at the 3-month follow-up.

Secondary Outcomes (Aim1a) Secondary Statistical Hypotheses: Those in both active intervention conditions will show greater improvements in overall pain severity, pain intensity (MCID and overall), pain-related interference (MCID and overall) and related quality of life outcomes (social role functioning, physical functioning, and patient global impression of change) relative to those receiving usual care at the 6- and 12-months follow-ups (secondary time points).

Analyses of secondary outcomes (Aim 1a) will follow the same proposed approach as Aim 1. Linear regression will be used to assess continuous outcomes and Poisson regression for binary and count outcomes. An interaction between intervention arms and time indicators will be included, and the primary time point for all secondary analyses will be 3 months following randomization; baseline levels of pain severity and all stratification variables will be included as covariates.

The RESOLVE Statistical Analysis Plan (SAP) provides details on these planned secondary outcome analyses.

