15.0. Secondary Effectiveness Analyses (Secondary Outcomes)

Secondary Outcomes (Aim1a) Primary Statistical Hypotheses: Those in both active intervention conditions will show greater improvements in overall pain severity, pain intensity (MCID and overall), pain-related interference (MCID and overall) and related quality of life outcomes (social role functioning, physical functioning, and patient global impression of change) relative to those receiving usual care at the 3-month follow-up.

Secondary Outcomes (Aim1a) Secondary Statistical Hypotheses: Those in both active intervention conditions will show greater improvements in overall pain severity, pain intensity (MCID and overall), pain-related interference (MCID and overall) and related quality of life outcomes (social role functioning, physical functioning, and patient global impression of change) relative to those receiving usual care at the 6- and 12-months follow-ups (secondary time points).

Secondary Outcomes (Aim 1a) Analyses: Aim 1a will examine the impact of the active interventions on secondary outcomes. Analyses of these outcomes will follow the same proposed approach as Aim 1. We will use linear regression for continuous outcomes and Poisson regression for binary and count outcomes. We will use GEE^{21,22} to estimate regression models for longitudinal data using an independence working correlation matrix. We will calculate all standard errors using the robust sandwich estimator^{21,22} to account for within-person and within-health coach correlation or any misspecified variance structures. We will include an interaction between intervention arms and time indicators, and the primary time point for all secondary analyses will be 3 months following randomization and will include as covariates baseline levels of pain severity and all stratification variables.

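### Secondary outcomes with directional hypotheses are each tested at 0.05, with error controlled only across the three arms; nothing covers the several outcomes and time points or ties secondary claims to the primary result

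*SAP*

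**What the plan says.** SAP 10.0 (Multiplicity) starts from a single primary endpoint: "We have one primary outcome: minimal clinically important difference (MCID) in pain severity at 3 months". For that endpoint it uses Fisher's LSD. In the first step, the "omnibus Wald test for any statistically significant difference between the three groups is evaluated at the 0.05 alpha level". Pairwise comparisons follow as a second step, "each using two-sided alpha=0.05, only if the omnibus test is statistically significant". For everything below the primary it adds one sentence: "secondary analyses will use a similar approach as that described for the primary outcome to control for the three group comparisons".

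SAP 15.0 then states hypotheses with a direction: "Those in both active intervention conditions will show greater improvements in overall pain severity". The same sentence goes on to pain intensity and interference (each as MCID and as a score), social role functioning, physical functioning and patient global impression of change, all relative to usual care. The 3-month set is labelled primary and the 6- and 12-month set secondary. Protocol 15.6 says the same and adds that "the primary time point for all secondary analyses will be 3 months following randomization". Protocol 15.3 sets one threshold for all results: "All confidence intervals and p-values will be two-sided and statistical significance at the 0.05 level".

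Neither document adjusts or orders tests across secondary outcomes or time points, makes them conditional on the primary test, or calls their p-values nominal. Exploratory outcomes form a separate, lower tier (SAP 3.3 and 17.0).

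**The concern.** LSD within an outcome deals with three arms being compared on that outcome. It does nothing about several outcomes being tested side by side, or about each being tested again at later visits. Here the secondary outcomes rank above the exploratory tier and carry stated expectations of benefit. Five of them are BPI-SF severity, intensity or interference scores, built from the same 11 items as the primary.

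The awkward case is a trial whose primary omnibus test fails while the continuous BPI-SF severity score, say, gives p<0.05. The plan does not say what may then be claimed. A pre-stated directional hypothesis met at the stated significance level could be reported as evidence that a program works. With this many tests, chance alone produces such a result far more often than the 0.05 level suggests.

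**Working it through.** **The per-outcome rule.** The documents give no familywise figure for the secondary outcomes, so there is none to reproduce. The sample size does confirm how the LSD rule works. With 15% under usual care and 22.5% in both active arms, requiring both the omnibus and the pairwise test gives 90% power at about 605 per arm and 90.8% at the planned 621. For retention, 621 / 0.80 = 776.25, rounded up to 777, and 777 × 3 = 2,331, as stated.

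**Counting the tests** (SAP 3.2 and 15.0). At 3 months there are MCID in intensity, MCID in interference, severity, intensity, interference, social role, physical function and PGIC. That is 8 outcomes, or 9 if the two PGIC items are tested separately, which the documents leave open. MCID in severity at 6 and 12 months adds two.
- 8 × 3 + 2 = 26
- 9 × 3 + 2 = 29

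**Independent tests.** The chance of at least one false omnibus rejection is 1 − 0.95^k.
- k = 8: 33.7%; k = 9: 37.0%
- k = 26: 73.6%; k = 29: 77.4%

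**Correlated tests.** Simulated trials with no true effect: three equal arms, an omnibus chi-square on 2 df at 0.05 per outcome, then pairwise |z| > 1.96. Two events are counted:
- (a) any omnibus rejection;
- (b) a rejection in which an active arm is significantly better than usual care, which is the event that the hypotheses concern.

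One outcome alone gives (a) 5.0% and (b) 2.1%. The correlations are assumptions. In each cell the 3-month figures run from 8 to 9 tests. The figures for all time points run over 26 to 29 tests and between-time correlation 0.5 to 0.7.

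| Between-outcome correlation | 3 months (a) | 3 months (b) | All times (a) | All times (b) |
|---|---|---|---|---|
| 0 | 34–37% | 15–17% | 64–73% | 35–42% |
| 0.3 | 30–33% | 13–15% | 59–68% | 29–34% |
| 0.5 | 26–27% | 11–12% | 51–59% | 24–29% |
| 0.7 | 20–21% | 9% | 40–47% | 19–22% |
| 0.8 | 16–17% | 7–8% | 34–39% | 15–18% |

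Repeat runs move a cell by up to about one point, so the ranges for all time points are quoted as about 33–73% for (a) and 15–42% for (b).

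**Uneven correlation.** A structure that builds the BPI-SF severity score from intensity and interference (correlated 0.5–0.7), links each MCID version to its score, and sets the other outcomes at 0.3–0.5 gives:
- 3 months: (a) 23–29%, (b) 10–13%
- all time points: (a) 46–62%, (b) 22–31%

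**When the primary omnibus test has not rejected.** With nine outcomes, a false 3-month secondary omnibus rejection still occurs in about 26% of trials at correlation 0.5 and 14% at 0.8.

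**The case against.** The best defense is that the hierarchy already exists: one primary outcome at one time point, then secondary, then exploratory outcomes, with 3 months named as the main time point. Many trials leave secondary outcomes unadjusted below a single primary, and whether to adjust is largely convention. SAP 10.0 is also candid that its control covers the three group comparisons, and no passage says that a secondary result may stand in for a failed primary. All of this stands. It is why the remedy is a statement of status and not a new testing procedure. It does not fill the gap, because no passage says that a secondary result may not be used in that way.

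A reader might infer three stronger things that the documents do not support.

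- **That the trial's main conclusion carries inflated error.** It does not: the primary is a single outcome, and LSD holds at 5.0% under no effect.
- **That the SAP promises familywise control for secondary outcomes and fails to deliver it.** It makes no such promise, so a ratio of the familywise rate to 0.05 would compare different quantities.
- **That one error rate, such as 27% at 3 months or more than half over all visits, follows from the plan.** Those values need between-outcome correlation near 0.5 or lower and count rejections in either direction, including differences between the two active arms. At correlation 0.7–0.8 the rate over all visits is 33–47%. False claims of benefit over usual care are roughly half as frequent as omnibus rejections, and in no setting examined do they reach 50%.

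**Conclusion.** The point holds as a gap in the secondary claims. Under the complete null, with between-outcome correlation from 0 to 0.8 and between-time correlation 0.5–0.7, at least one false omnibus rejection occurs in about 16–37% of trials at 3 months and 33–73% over all time points. A false claim that an active arm beats usual care occurs in about 7–17% and 15–42%. Against 2.1% for one outcome, the 3-month rate is about three to eight times as high (7.0 / 2.1 = 3.3; 17.1 / 2.1 = 8.1).

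The ranges rest on assumed correlations, on 8 or 9 tests per visit, and on counting all time points as one family for the larger figures. Since five outcomes share BPI-SF items, correlation among those five is probably high, which argues against the top of each range. No setting examined brings the benefit-only rate down to the single-outcome level. The gap is worth closing before unblinding, but it does not threaten the primary result.

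**What to change.** Add to SAP 10.0, and repeat in SAP 15.0, wording such as: *Only the 3-month comparison of MCID in pain severity is confirmatory. Secondary outcomes, and the 6- and 12-month time points, are supportive. They are reported as estimates with 95% confidence intervals and nominal p-values, and will not be used to claim effectiveness if the primary omnibus test is not significant.*

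Under the complete null, effectiveness claims can then arise only in the 5% of trials where the primary omnibus test rejects, and a false confirmatory claim of benefit arises in about 2%. If the primary effect is real, error across the secondary outcomes remains uncontrolled, which is why they should stay labelled supportive.

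The cost is a few sentences, with no new data and no change to the primary test. SAP 2.0 allows SAP changes, gives the SAP precedence, and requires a matching protocol amendment only when the primary endpoint or its analysis changes. Aligning Protocol 15.6 is therefore tidy but not required. The real downside is that a true secondary effect could not be claimed as confirmed when the primary fails.

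Holm adjustment across the 3-month secondary outcomes is optional and not part of this fix. It would lower the average power of a secondary outcome from 80% to about 62% when all nine have an effect, and it would leave the later time points unadjusted.
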